1. GENERAL STATISTICAL PLAN

The data analysis plan *a priori* defines a primary intent-to-treat (ITT) population, a set of secondary evaluation populations, a primary outcome measure, a set of secondary outcome measures, a single primary evaluation time point, a secondary evaluation time point, a primary statistical analysis methodology, a criterion for statistical significance, and guidance for interpretation of results.

The **primary ITT population** is defined as all participants who complete a training set-up visit. Note that this includes all randomized participants except those who drop/withdraw post-randomization and pre-setup visit.

The **primary outcome measure**, per determination of an independent external review committee comprised of experts in the diagnosis and evaluation of the trial target population (i.e., individuals with hemispatial neglect following acquired brain injury), is the Posner cueing task; a spatial attention measure that captures the visual *Field Bias* score (average reaction time to Left trials – average reaction time to Right trials), as reported here:

Rengachary, J., d'Avossa, G., Sapir, A., Shulman, G. L., & Corbetta, M. (2009). Is the posner reaction time test more accurate than clinical tests in detecting left neglect in acute and chronic stroke?. *Archives of physical medicine and rehabilitation*, 90(12), 2081-2088.

To capture a valid assessment of participants' performance in the Posner cueing task (*Field Bias* score) independent of criterion shifts or speed-accuracy trade-offs [Lange-Malecki and Treue, 2012; Spence et al., 2001; Teufel et al., 2010], we will employ an inverse efficiency scoring approach (IES; Townsend and Ashby, 1983) to account for potential differences in accuracy across Left and Right trial types (e.g., Valid and Invalidly cued trials). Mean reaction times (RTs) will be divided by the proportion of correct trials responded to in each specific condition.

The **secondary outcome measures** will evaluate training exercise-based progress, as well as performance in several measures identified by domain, including: spatial attention, spatial cognition, cognitive performance, functional ability, quality of life, and quality of sleep.

Spatial Cognition

- Greyscales Task (raw scores)
- Posner Cueing Task (raw scores)
- Spatial Working Memory Task (raw scores)

Cognitive Performance

- DKEFS Verbal Fluency Letter Fluency (raw scores)
- DKEFS Verbal Fluency Category Fluency total (raw score)

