- DKEFS Verbal Fluency Category Switching total (raw score)
- DKEFS Verbal Fluency Category Switching accuracy total (raw score)
- WAIS-IV Digit Span total (sum of forward, backward, sequencing raw scores)
- WAIS-IV Digit Span Forward total (raw scores)
- WAIS-IV Digit Span Backward total (raw scores)

- WAIS-IV Digit Span Sequencing total (raw scores)
- Continuous Performance Task (raw scores)

Functional Ability

- Catherine Bergego Scale total (raw score)
- Barthel Index total (raw score)

Quality of Life

- SF-12 Physical Composite Score
- SF-12 Mental Composite Score

Quality of Sleep

- Pittsburgh Sleep Quality Index total (sum of component scores)
- Pittsburgh Sleep Quality Index Sleep Efficiency (raw score)

The **primary analysis time point** is V2, the post-training assessment. The **secondary analysis time point** is V3, the follow-up assessment.

The **primary statistical analysis methodology** is a linear mixed-effects model approach. We will first compare treatment and active control groups in the ITT population to determine if any differences in baseline demographic, characterization, outcomes variables, or total program use time remain after the randomization process. Any such factors that show trend level significant differences ($p < 0.1$) will be noted and used as covariates in the linear mixed model analysis. We will examine the data from each outcome measure using a linear mixed model with group and time as fixed factors, site as a random factor, and co-variates as necessary from the baseline analysis. Missing data will be handled with an iterative maximum likelihood procedure to optimally estimate model parameters. The key value for significance will be the group-by-time interaction factor for the model. This modeling will be conducted with a Type I error set at 0.05 for each model.

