Secondary, exploratory analysis will test for effects in exercise-based progress as well as by domain (e.g., working memory, attention, processing speed) to determine the unique benefit in each area of attention, cognition and independent function. First, to determine if the treatment effect varies based on participants' clinical severity of neglect (Mesulam total misses) or symptom subtype (e.g., sensory loss vs. intact sensory systems), we will correlate neglect severity (or subtype(s)) with gain scores on composite spatial cognition or executive performance and composite functional performance (as well as individual assessment measures). Additionally, we will measure whether improvements on certain components of the training program (e.g., improvements at inhibiting one's response to target stimuli) are associated with composite attention, executive or functional performance scores (as well as individual assessment measures). This could indicate whether certain patterns of training improvements are related more to improvements in attention, executive or functional performance. These analyses will be evaluated after correcting for multiple comparisons (i.e., Bonferroni).

The **criterion for statistical significance** is $p < 0.05$. Results greater than $p = 0.05$ and less than $p = 0.11$ will be described as trends.

To evaluate the effect of the experimental software treatment program (incorporating TAPAT) on spatial attention) we will conduct the analysis based on the pre-training (baseline) and post-training data.

Finding a significance level of $p < 0.05$ on the primary outcome measure will support the statement that the intervention improves spatial attention in the population.

To evaluate the endurance of effects following completion of the experimental software treatment program (incorporating TAPAT) we will use the same modeling approach based on the pre-training assessment (baseline) and end of study (follow-up visit) assessment data using a mixed-effects model parallel to those used to meet the primary and secondary aims. Finding a significance level of $p < 0.05$ on the primary measure will support the hypothesis that the training drives persistent improvement in spatial attention above and beyond an active control.

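### If baseline Field Bias trips the p<0.1 screen it becomes a covariate for itself; as a main effect this does not correct the imbalance in the group-by-time estimate and can make its standard error too small

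*SAP*

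**What the plan says.** All of this stands in SAP section 1, General Statistical Plan.

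- **Screen.** The arms are compared to see whether "differences in baseline demographic, characterization, outcomes variables, or total program use time remain after the randomization process". The next sentence sets the threshold at p<0.1 ("Any such factors that show trend level significant differences") and the consequence: such factors "will be noted and used as covariates in the linear mixed model analysis".
- **Model.** Each outcome is analysed by a "linear mixed model with group and time as fixed factors, site as a random factor". No participant effect is named. The form in which a covariate enters (main effect, or also crossed with time) is not given.
- **Decision.** "The key value for significance will be the group-by-time interaction factor for the model".
- **Time levels.** For the effect on spatial attention, "we will conduct the analysis based on the pre-training (baseline) and post-training data".
- **Primary outcome.** Posner Field Bias, that is "average reaction time to Left trials – average reaction time to Right trials".

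No exception is made for an outcome's own baseline. Nothing sets the baseline means equal across arms, and nothing adjusts for baseline regardless of the screen.

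**The concern.** Field Bias is an outcome variable, so the screen covers its baseline value. That value is also half of the response data in the primary model. If the arms differ on it, the rule puts the same measurement on both sides of the equation.

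A covariate that is constant over time acts on both visits equally and drops out of a change. The remedy therefore appears to be applied while the tested estimate stays as it was. That estimate is exposed to regression to the mean: with no treatment effect, the arm that starts with the higher Field Bias tends to show the larger fall. The plan lets p<0.05 on this one measure support its claim about spatial attention. A result obtained alongside a visible baseline difference would therefore be open to challenge, with no effective pre-specified answer.

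**Working it through.** **Inputs.** From SAP section 1: screen at p<0.1, response at baseline and V2, interaction test, and the error level ("This modeling will be conducted with a Type I error set at 0.05 for each model"), taken as two-sided. Assumed, because the SAP does not give them: baseline-V2 correlation rho of 0.4, 0.6 or 0.8, and 40 per arm for the fitted example and simulation. Also assumed: equal variances, complete data, no treatment effect. The SAP has no figure of its own to reproduce here.

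**1. How often the screen trips.** Under randomisation, baseline Field Bias gives p<0.1 in 10% of trials, i.e. |z_b| > 1.645.

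**2. The estimate.** The interaction is (mean change in one arm) minus (mean change in the other). A main-effect covariate b adds beta × b at both visits and cancels. In a fitted example (rho 0.5, true effect zero, baseline shift of 0.5 SD built in) the interaction was -0.374 without baseline as covariate and -0.374 with it, whether participant or site was the random factor. Analysis of covariance on the same data gave -0.191.

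**3. Error of the change-score test given imbalance.** Given z_b, the test statistic is normal with mean -sqrt((1-rho)/2) × z_b and variance (1+rho)/2. At z_b = 1.645 the shift is sqrt(0.3), sqrt(0.2) or sqrt(0.1) times 1.645, i.e. 0.90, 0.74 or 0.52 standard errors. The rejection rate there is 10.3%, 8.7% or 6.9%. Integrating over all |z_b| > 1.645 gives row A of the table.

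**4. What entering baseline does to the standard error.** With no participant effect, or a random intercept that falls to zero, the fitted slope is (1+rho)/2 and the pooled residual variance is (3+rho)(1-rho)/4 in units of the outcome variance. The standard error is then sqrt((3+rho)/4) of the correct one for a change score: 0.922, 0.949 or 0.975. The effective critical value falls from 1.96 to 1.81, 1.86 or 1.91. Repeating the integration gives row B. In the fitted example the standard error fell from 0.207 to 0.196 with a participant intercept, and from 0.278 to 0.195 with site only.

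| Two-sided false-positive rate, no true effect | rho 0.4 | rho 0.6 | rho 0.8 |
|---|---|---|---|
| A. Screen tripped, change-score test | 16.7% | 12.8% | 8.9% |
| B. Screen tripped, baseline entered as own covariate | 21.5% | 15.3% | 9.8% |
| C. Screen not tripped, change-score test | 3.70% | 4.14% | 4.57% |
| Overall, change-score test: 0.1A + 0.9C | 5.0% | 5.0% | 5.0% |
| Overall, two-stage rule: 0.1B + 0.9C | 5.5% | 5.3% | 5.1% |

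**5. Check by simulation** (40,000 null trials, 40 per arm). At rho 0.3, 0.5, 0.7 and 0.9, trials that tripped the screen rejected in 18.2%, 14.2%, 10.9% and 7.1% for the change-score test, and in 25.5%, 18.7%, 13.1% and 8.1% with baseline entered. The same formulas give 18.8%, 14.8%, 10.8%, 6.9% and 25.1%, 18.3%, 12.4%, 7.3%, so agreement is within a point. Analysis of covariance gave 5.0% throughout.

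**6. Precision.** Baseline-adjusted variance over change-score variance is (1-rho²)/(2(1-rho)) = (1+rho)/2, which is 0.70, 0.80 or 0.90.

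**The case against.** **The test is valid on average.** A group-by-time contrast in a randomised trial is unbiased and, without the screen, holds 5% over all randomisations. The excess in trials that trip the screen is offset by rates below 5% in the rest. This stands. A reader might infer from the conditional rates that the primary test is invalid or grossly inflated; the overall rows of the table do not support that.

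**The site-only reading is not liberal overall.** If site really is the only random factor, the uncorrected standard error before any covariate is too large by 1/sqrt(1-rho), and the test is conservative. At rho 0.4 the critical value becomes 1.96 × 1.29 = 2.53, which a standard normal exceeds in absolute value 1.1% of the time. The overall rate is then at most 0.1 × 21.5% + 1.1% = 3.3%. This also stands, but it means that tripping the screen turns a conservative test into a liberal one in exactly the trials with imbalance.

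**The rule has other uses.** It is tempting to say that the covariate rule fails in the one case it is meant for. The SAP does not support that: the rule also covers demographic and characterization variables and programme use time.

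**The covariate form is open.** The SAP does not say main effect only, and a covariate-by-time term would change the interaction estimate. The exact invariance also needs complete data; with missing V2 values under maximum likelihood the coefficient can move somewhat. Both limits stand. The plain reading of a covariate is a main effect, and leaving the form open does not repair it.

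**The precision gain can be small.** It is 10% at rho 0.8 and 5% at 0.9. That is correct, but it costs nothing.

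**Conclusion.** The point holds as a conditional one and should be corrected; it does not invalidate the primary test. For an outcome's own baseline, the screening step as a main effect leaves the tested estimate uncorrected, and in a model without an effective participant term it understates the standard error. Among null trials that trip the screen the false-positive rate is roughly two to four times the nominal 5% over rho 0.4 to 0.8, while the overall rate is about 5.0% to 5.5% when the untripped trials are tested with a participant-level error term. The rest of the cost is precision that the collected baseline could supply.

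The direction holds for every rho below 1. The sizes depend on rho, which is assumed, and on equal variances and complete data. The closed-form rates are large-sample and do not depend on the assumed 40 per arm.

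**What to change.** For the primary and each secondary outcome, always adjust for that outcome's own baseline, whatever the observed difference. Either form serves:

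- a repeated-measures model with a common baseline mean across arms, the test being the arm difference at V2 (or V3); or
- V2 (and V3) modelled on arm with baseline as covariate.

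Take outcome variables out of the p<0.1 screen and report baseline differences descriptively. If the repeated-measures form is chosen, state the participant-level covariance explicitly.

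The cost is SAP wording and model code before unblinding. No new data are needed, the comparison of arms at V2 is kept, and the variance falls for any rho below 1. The rest of the screen, including programme use time, which arises after randomisation, is a separate matter that this change does not settle.

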To identify specific populations of treatment responders and non-responders) we will conduct exploratory data analyses post-hoc to examine predictors of treatment gain and predictors of lack of treatment gain based on baseline participant demographic, cognitive, and functional measures, as well as on learning rate and plateau performance measures derived over the course of the experimental software treatment program (incorporating TAPAT) use. We will initially employ single regression models to identify variables that predict change in cognitive and functional assessments, and then use generalized linear modeling to explore combinations of predictors of treatment gain or lack of gain.

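### Correlating neglect severity or subtype with gain scores does not test whether the treatment effect varies; a group interaction is needed

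*SAP*

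**What the plan says.** All the relevant text is in SAP section 1, General Statistical Plan.

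- Aim of the secondary, exploratory analysis: "to determine if the treatment effect varies based on participants' clinical severity of neglect (Mesulam total misses) or symptom subtype".
- Method, in the same sentence: "we will correlate neglect severity (or subtype(s)) with gain scores on composite spatial cognition or executive performance and composite functional performance". Individual assessment measures are to be handled the same way. The arms included are not stated.
- Multiplicity: "These analyses will be evaluated after correcting for multiple comparisons (i.e., Bonferroni".
- The main mixed model has group and time as fixed factors, site as a random factor, and covariates chosen from baseline imbalance. Its decision rule is: "The key value for significance will be the group-by-time interaction factor for the model".
- The follow-up claim is also comparative: "the training drives persistent improvement in spatial attention above and beyond an active control".
- The later responder analysis uses "single regression models to identify variables that predict change in cognitive and functional assessments", again with no group term.

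The spatial-bias population under Analysis Populations is a subset defined by Posner field bias. It does not test modification by severity or subtype.

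**The concern.** In a trial with an active control, the treatment effect is a difference between arms. Asking whether it varies with severity means asking whether that difference changes with severity. The SAP keeps the between-arm contrast for its main claims and drops it for this question.

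Severity can relate to gain for reasons unrelated to treatment: recovery or practice that depends on severity, true scores that revert, or baseline error shared by the severity test and the outcome. Each can produce a correlation with gain when every patient benefits equally. If the shared change runs against a real modification, the correlation can miss it. The same reasoning applies to subtype, where gains would be compared between subtypes without reference to the control arm.

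At stake is a statement about which patients benefit more. Such a statement could rest on prognosis alone, or a real difference could go unreported.

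**Working it through.** **What each analysis estimates.** Let s be standardised severity, g the arm (0 or 1), and

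gain = a + b·g + c·s + d·g·s + error.

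Variation in the treatment effect is d. With 1:1 arms:

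- the pooled correlation tests c + d/2;
- the correlation in the treated arm alone tests c + d;
- only the group-by-severity term tests d. With two visits and complete data it equals group × time × severity in the mixed model.

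The correlations answer the stated question only if c = 0, and nothing in the SAP supports that.

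**Inputs.** The SAP gives no sample size, SD or correlations, so there is no planned figure to reproduce. All of these are assumed: 30 per arm, outcome SD 1, constant effect 0.5 SD (d = 0), V1–V2 correlation ρ = 0.7, severity–baseline correlation r, two-sided tests, no site effect.

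**Hand check (Fisher z).**

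*Severity related to V2 only through V1, r = 0.5.* The covariance of s with gain is −(1 − ρ)r = −0.3 × 0.5 = −0.15. The within-arm gain variance is 2(1 − ρ) = 0.6. Pooling adds 0.5² × 0.25 = 0.0625, giving 0.6625.

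- Pooled: |corr| = 0.15/√0.6625 = 0.184; atanh(0.184) × √57 = 1.41; P(Z > 1.96 − 1.41) ≈ 29%.
- Treated only: |corr| = 0.15/√0.6 = 0.194; atanh(0.194) × √27 = 1.02; about 17%.

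*Stable true score, plus recovery of 0.2 SD per SD of severity in both arms.* The covariance is 0.2. The variance is 0.6 + 0.04 = 0.64 within arm and 0.7025 pooled.

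- Pooled: |corr| = 0.239; z mean 1.84; about 45%.
- Treated only: |corr| = 0.25; z mean 1.33; about 26%.

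**Simulation, 10,000 runs per case, no true variation, rejection at 0.05:**

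| Case | Pooled | Treated only | Group × severity on gain |
|---|---|---|---|
| Through V1 only, r = 0.5 | 28.8% | 17.2% | 4.9% |
| Through V1 only, r = 0.3 | 13.2% | 9.4% | 5.1% |
| Stable true score, independent errors, r = 0.5 | 5.2% | 5.1% | 5.3% |
| Same, plus shared slope 0.1 | 15.5% | 10.9% | 5.3% |
| Same, plus shared slope 0.2 | 45.7% | 27.0% | 5.0% |

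**With the planned Bonferroni correction, per test (pooled / treated only).** The number of tests is not listed. SAP section 4 gives 2 spatial, 9 cognitive and 2 functional measures. If the executive composite means Cognitive Performance, that is 13 measures plus 3 composites = 16, and 16 × 2 (severity and subtype) = 32. The 32-test column uses 20,000 runs per case.

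| Case | 3 tests (nominal 1.7%) | 10 tests (0.5%) | 32 tests (0.16%) |
|---|---|---|---|
| Through V1 only, r = 0.5 | 16% / 8% | 7% / 3% | 3.6% / 1.4% |
| Through V1 only, r = 0.3 | 6% / 4% | 2.4% / 1.3% | 1.1% / 0.5% |
| Shared slope 0.1 | 8% / 4% | 3.3% / 1.5% | 1.2% / 0.5% |
| Shared slope 0.2 | 29% / 15% | 17% / 7% | 9.0% / 3.0% |

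**Missed variation.** Let d = 0.5 and c = −0.25. The pooled slope is −0.25 + 0.5/2 = 0, so the pooled correlation has nothing to find. Detection at 0.05 is 6% pooled, 39% treated only and 66% for the interaction. The treated-only version fails when c + d = 0. With slope −0.5 in controls, 0 in treated patients and residual gain SD 1, it detects the variation in about 5% of trials. The interaction detects it in 30% to 84% for total N of 40 to 150.

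**The case against.** The strongest reply has four parts.

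1. **Silence on the arms is not error.** Correlations could be run per arm and then compared, which would address the question. But that comparison is written nowhere, and neither a pooled nor a treated-only correlation answers the stated aim.
2. **The stakes are low.** The analysis is exploratory and Bonferroni-corrected, and the claims rest on the group-by-time test. This stands, and it limits the consequence. Bonferroni moves the threshold but leaves the estimated quantity unchanged; in the shared-change cases the corrected rates stay well above nominal.
3. **The inputs are chosen.** This also stands. Severity is a cancellation count, while many outcomes are fluency or digit-span tests, for which r = 0.5 may be too high. At r = 0.1 the through-V1 case gives 5.8% pooled and 5.7% treated only, close to nominal. Under a stable true score with independent errors there is no inflation. Subtype was not simulated.
4. **The interaction costs power.** If controls show no severity-related change and d = 0.5, the treated-only correlation detects 90% at 0.05 against 65% for the interaction. The figures are 65% against 32% with 10 tests, and 49% against 20% with 32. The loss is real. But the treated-only result can be read as variation in the treatment effect only if control change is unrelated to severity, which that analysis does not check.

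**Conclusion.** The concern holds. The stated aim is effect modification and the stated method is a correlation with change, and the SAP supplies no between-arm term to connect them. That conclusion needs no numerical assumption and applies to severity and subtype alike.

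The size does depend on assumptions. For continuous severity with 30 per arm, false signals at uncorrected 0.05 range from 5% (no shared change) to 46% pooled or 27% treated only (shared slope 0.2). At a 32-test Bonferroni level the shared-change cases shown give 1.1% to 9.0% pooled, against 0.16%. The interaction test holds about 5% at the 0.05 level throughout. The primary analysis is untouched, so this should be corrected but does not threaten the trial's main result.

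**What to change.** In SAP section 1, replace the correlation with one model using both arms of the ITT population. The choice closest to the existing plan is to add severity (or subtype) and its interactions to the mixed model on V1 and V2 and test group × time × severity, without also entering the baseline outcome as a covariate. The alternative, not in addition, is a V2 model with the baseline outcome as covariate and a group × severity term. It had somewhat more power in the simulation with no shared change (73% against 65% at 0.05). Name one of the two in advance.

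Report the interaction estimate with its 95% confidence interval, list the tests counted in the Bonferroni correction, and label the result exploratory. Plain correlations may stay as descriptions of prognosis.

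In the responder paragraph, apply the same interaction to baseline predictors measured in both arms before calling them predictors of benefit from treatment. Keep learning-rate and plateau measures from the experimental program descriptive.

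The cost is SAP wording and the added severity or subtype terms in each model, with no new data. The price is the lower power given above. At the assumed size a non-significant interaction would often be uninformative, which is why the interval matters.

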population that completed a V3 or delayed follow up visit (the ITT-FEV3 population). Note that a participant may complete a specific visit but have missing data for a test in which case the participant is in the overall FE population but does not contribute data to the FE population for that visit, e.g., the number of evaluable cases for a specific test on a specific visit may be smaller than the FE population for that visit because of missing data.

- v. *Intent to Treat (ITT) Fully-Trained (FT) population:* This is a secondary analysis population, defined as including all members of the ITT-FE population who complete a target number of training visits (32 visits). Note that the FT populations are strict subsets of the FE populations; a person who completes the target number of training visits but does not complete the evaluation visit is not a member of the FT population.
- vi. *Intent to Treat (ITT) Spatial-Bias (SB) population:* This is a secondary analysis population, defined as including all members of the ITT population who demonstrate a bias in spatial attention that is numerically greater on the ipsilesional side of space on the primary outcome measure (Posner cueing task – field bias).

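### The endurance model leaves out V2, so it does not protect the V3 contrast if return at V3 depends on V2 performance differently by arm

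*SAP*

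**What the plan says.** All of this is in SAP section 1 (General Statistical Plan) unless noted.

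- **Time points.** The primary time point "is V2, the post-training assessment"; the secondary one "is V3, the follow-up assessment". Section 4 calculates composite scores at V1, V2 and V3, so all three visits are available.
- **Primary model.** For the treatment effect, "we will conduct the analysis based on the pre-training (baseline) and post-training data". This is a two-visit model.
- **Endurance model.** For persistence, "we will use the same modeling approach based on the pre-training assessment (baseline) and end of study (follow-up visit) assessment data". This is a second two-visit model, and V2 is not in it. The SAP describes it as run "using a mixed-effects model parallel to those used to meet the primary and secondary aims".
- **Terms.** Each outcome is analysed with a "linear mixed model with group and time as fixed factors, site as a random factor, and co-variates as necessary from the baseline analysis". Site is the only random term named.
- **Missing data.** "Missing data will be handled with an iterative maximum likelihood procedure to optimally estimate model parameters". The SAP gives no other method and no sensitivity analysis for V3 dropout.
- **V3 population.** Under Analysis Populations, the only V3-specific set is the part of the ITT "population that completed a V3 or delayed follow up visit (the ITT-FEV3 population"). It is a completer set.
- **Claim.** A result below 0.05 on the primary measure in the endurance model is to be read as support for a lasting gain over the active control.

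**The concern.** Maximum likelihood accounts for dropout only through the variables in the fitted model. A participant who attends V2 and then leaves has a post-training score on file, but the endurance model cannot use it. If the chance of returning at V3 depends on that score, V3 is missing at random given baseline and V2. It is not missing at random given baseline, group, site and the selected covariates alone.

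An effect on the group-by-time term needs a second condition: the V2-related loss must shift the two arms by different amounts. A treatment effect at V2 can do this under one common dropout rule, and so can a dropout rule that differs between arms. The ITT-FEV3 set is no safeguard, because restricting to completers carries the same selection.

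At stake is the claim of persistence at V3. Depending on the pattern, a real lasting effect could be understated, or an apparent one inflated or created.

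**Working it through.** **Figure to reproduce.** There is none. The SAP gives no sample size, effect size, SD, correlation or dropout rate. All inputs below are assumptions.

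**Inputs.** Unit SD at each visit, with a lower score better. Correlations are V1–V2 0.6, V1–V3 0.5 and V2–V3 0.8. The treatment effect is -0.5 at V2 and -0.30 at V3. V3 is missing with logit(p) = -1.4 + b × V2, where b is set per arm. At b = 0 the loss is 1/(1 + e^1.4) = 20%.

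**Step 1: what each model uses to predict V3.**
- Baseline only: weight on V1 = 0.5.
- Baseline and V2: weight on V2 = (0.8 - 0.6 × 0.5)/(1 - 0.6²) = 0.50/0.64 = 0.78; weight on V1 = 0.5 - 0.6 × 0.78 = 0.03.

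Under these correlations nearly all the information about a missing V3 score lies in V2, which the planned model excludes.

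**Step 2: V3 contrast in large samples** (simulation with 400,000 or more per arm; regression equivalent to maximum likelihood, fitted within arm; truth -0.30).

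| V2-dependence of dropout (b treated / b control) | Lost, treated / control | Baseline + V3 | Baseline + V2 + V3, unstructured |
|---|---|---|---|
| none (0 / 0) | 20% / 20% | -0.30 | -0.30 |
| common, weaker (0.5 / 0.5) | 17% / 21% | -0.29 | -0.30 |
| common (1 / 1) | 17% / 24% | -0.27 | -0.30 |
| steeper in treated (1 / 0.5) | 17% / 21% | -0.32 | -0.30 |
| treated only (1 / 0) | 17% / 20% | -0.38 | -0.30 |

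Under the common rule at slope 1 the bias is 0.03 SD against treatment (0.03/0.30 = 10% of the effect). In the treated-only case it is about 0.075 SD in favour of treatment (0.075/0.30 = 25%). With a common rule and no V2 effect the bias is nil. In the treated-only case, lowering the V2–V3 correlation to 0.7 or 0.6 gives -0.36 or -0.34.

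**Step 3: other dropout rates** (V2–V3 correlation 0.7; bias of the two-visit model in SD at 10% / 25% / 40% average dropout).
- Dropout unrelated to V2, or a common rule with no V2 effect: about 0.
- Common rule with a 0.5 SD benefit at V2: 0.015 / 0.026 / 0.03 at slope 1 and 0.036 / 0.064 / 0.080 at slope 2, all against treatment.
- Poor V2 performers leaving only the treated arm, no true effect: -0.047 / -0.096 / -0.146, a false benefit.
- Opposite rules in the two arms, no true effect: -0.076 / -0.177 / -0.281.
- Three visits with unstructured covariance: within 0.004 of the truth throughout.

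**Step 4: effect on the test.** Assume 40 completers per arm and a two-sided 5% test. The standard error is √(2 × (1 - 0.5²)/40) = 0.19. A bias of 0.1 SD then raises the error rate to about 8%, and 0.2 SD to about 18%.

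**Step 5: the covariance matters.** In the treated-only case of step 2, a three-visit model with site as the only random term returns the completer contrast, -0.42. A random participant intercept gives about -0.33. Only the unstructured form gives -0.30.

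**Step 6: precision.** With dropout unrelated to the scores, the variance of a V3 arm mean is proportional to (1 - R²)/(1 - q) + R², where q is the dropout rate. R² is 0.25 with V1 alone and (0.25 + 0.64 - 2 × 0.5 × 0.8 × 0.6)/0.64 = 0.64 with V1 and V2. At q = 20% the standard error ratio is √(1.090/1.188) = 0.96, a gain of 4%. At q = 10% the gain is 2%, and with no dropout it is nil.

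**The case against.** A reader might infer that the endurance result will be biased. The SAP does not support that. It gives no V3 dropout rate and no reason for dropout, and nothing in it ties a left-minus-right reaction-time score to attendance. If dropout is unrelated to V2 given the modelled variables, the two-visit contrast is valid and targets the same V3 effect. Under a common dropout rule the bias is small and works against treatment, so it would not create a false claim of persistence. The -0.38 figure needs dropout to depend on V2 in one arm only. All of this stands, and it is why the point is conditional and the size is a range.

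A reader might also infer that the model ignores the training period altogether. That goes too far: group is in the model, and total program use time becomes a covariate if the arms differ on it at p < 0.1. Neither replaces the participant's own V2 score. An argument from wasted precision is also weak, since the gain is only 2–4% at 10–20% dropout.

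Finally, the primary V2 conclusion is untouched, and V3 is the secondary time point. That limits the importance of the point but does not remove it, because the SAP attaches an explicit claim to the V3 test and offers no other safeguard against V2-related dropout.

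**Conclusion.** The point holds as a conditional weakness of the secondary V3 analysis. The SAP chooses a model that cannot use V2 and relies on maximum likelihood alone. The V3 contrast is therefore unprotected if return depends on V2 and this acts differently by arm. Under the assumptions of step 2, with 17–24% lost, the two-visit estimate runs from about -0.27 to -0.38 against a true -0.30. Across the wider assumptions of step 3 the bias runs from nil to about 0.28 SD, and the top of that range needs opposite dropout rules and 40% loss. Neither direction nor size can be fixed from the SAP. The change is worth making because it costs little and, where dropout is unrelated to V2, introduces no bias.

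**What to change.** For the endurance question, fit baseline, V2 and V3 in one mixed model with visit as a categorical factor, group-by-visit terms, site as a random factor, the same covariates as planned, and an unstructured within-participant covariance. Test the baseline-to-V3 group-by-time contrast from that model. State the covariance explicitly, because adding V2 with site as the only random term would not help (step 5). The primary baseline-to-V2 analysis can stay as specified.

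The cost is a change of SAP wording and a few more covariance parameters to estimate; no new data are needed. The change covers dropout that depends on recorded scores. It does not cover dropout that depends on the unseen V3 score itself, or participants who miss V2 as well.
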